5.4. Measure of health motivation in food choices

The **Food Choice Questionnaire**, developed by Steptoe et al. (1995), measures the motives related to food choice, including health. We will use the ‘Health’ and ‘Weight control’ subscales of this questionnaire [24].

5.5. Measure of physical activity level

The **International Physical Activity Questionnaire – Short Version** (IPAQ-SF) will be used to assess the physical activity level. The IPAQ-SF includes 7 items and records the activity of four intensity levels: 1) vigorous-intensity activity such as aerobics, 2) moderate-intensity activity such as leisure cycling, 3) walking, and 4) sitting [25]. Although the original authors recommended to ask about the last 7 days of recalled physical activity, due to the context in which this study will be run, i.e., self-isolation of UK population due to COVID-19 propagation preventive measures, we will ask about a usual week of recalled physical activity: number of days per week and how much time per day a participant usually does each of the four types of activity.

5.6. Familiarity and liking of the test foods

Participants will be presented with the picture of the 600 kcal portion of each food, as UK public health guidelines recommend energy consumption ≤ 600 kcal for a main meal [26], and asked:

- “Have you ever eaten this food?” Answers: yes or no (*familiarity*)
- “How much do you like this food?” Answers on a 100-point visual analogue scale (anchors: not at all, extremely) (*liking*) [21]

6. STUDY FLOW

RECRUITMENT (Prolific)	
 ▪ Predefined screening questions of Prolific website will be used to target the sample (Appendix B) ▪ Participants who meet the inclusion/exclusion criteria will be emailed by Prolific and/or offered to complete our study on their Prolific account (Appendix C) ▪ Eligible participants who want to take part on the study will click on the start button and be redirected to our study website (Inquisit)
INFORMED CONSENT	
 ▪ Participants will read the information sheet (Appendix D) ▪ Participants who want to proceed will tick a consent box (Appendix E)
RANDOMISATION	
 ▪ Participants will be equally randomised and allocated to one of the four experimental groups using Inquisit software
BASELINE ASSESSMENTS	
 ▪ Participants will complete a baseline questionnaire on demographics (Appendix G)
MEAL CHOICE TASK	
 ▪ Instructions will be displayed (Appendix H) ▪ Meals will be displayed in randomised order

	Energy labelling (kcal+/PACE-)	PACE labelling (kcal-/PACE+)	Energy and PACE labelling (kcal+/PACE+)	No labelling (kcal-/PACE-)
EXECUTIVE FUNCTION	Tasks randomised in order: 
 ▪ Inhibition (Stroop task) ▪ Working memory (backwards digit-span task) 			
HEALTH MOTIVATION	
 ▪ Health and weight control subscales from the Food Choice Questionnaire (Appendix I) 			
PHYSICAL ACTIVITY LEVEL	
 ▪ International Physical Activity Questionnaire – Short Version (IPAQ-SF) (Appendix J) 			
FAMILIARITY AND LIKING	
 ▪ For each dish: 
 ○ Familiarity (Appendix K) ○ Liking rating (Appendix L) 			
DEBRIEFING QUESTIONNAIRE	
 ▪ Aim guessing in an open-ended response format (Appendix M) ▪ Questionnaire (Appendix M) 			
ADDITIONAL MEASURES	
 ▪ Interoception preliminary survey¹ (Appendix N) 			
DEBRIEFING TEXT	
 ▪ Tell the participants what the study was about (Appendix O) 			
DATA MANAGEMENT	
 ▪ The result files will contain: 
 ○ Participant unique ID ○ Experimental condition participant is directed to ○ Amount of self-served food ○ Answers to questionnaires 			

7. STATISTICAL ANALYSES

All statistical analyses will be performed using SAS version 9.3 (SAS Institute, Inc., 2012 SAS® 9.3. Cary, NC). The level of significance will be set at $p < 0.05$ for the main and sensitivity analyses, $p < 0.01$ for secondary analyses and $p < 0.001$ for exploratory analyses unless otherwise specified. Linear mixed models will be fitted with PROC MIXED.

7.1. Variables description

Primary outcome

The main outcome variable is the **total self-served energy** (in kcal).

Other outcomes:

Derived from the debriefing questionnaire:

1. Kcal influence (item 1): whether kcal content influences the quantity of self-served food;
2. PACE influence (item 2): whether physical activity energy equivalent influences the quantity of self-served food.

Answers to each item will be coded as: 1 = Strongly disagree; 2 = Disagree; 3 = Slightly disagree; 4 = Neutral; 5 = Slightly agree; 6 = Agree; 7 = Strongly agree.

Independent variables

SEP

¹ These data are collected to inform a future study and will not be analysed as part of this study.

Highest educational qualification will be coded from 1 to 9: 1 = No formal qualifications; 2 = 1–3 GCSEs; 3 = 4+ GCSEs; 4 = A level; 5 = Certificate of higher education (CertHE); 6 = Diploma of higher education (DipHE); 7 = Bachelor; 8 = Master's degree; 9 = Doctorate, and as a binary variable as *lower* (values: 1, 2, 3, 4) or *higher* (values: 5, 6, 7, 8, 9).

Years in higher education, as a continuous variable.

Level of education (composite score): Assuming that highest educational qualification and years in higher education will be significantly correlated (tested using Pearson's r), we will z-score the two variables and create an average of the two to form a level of education composite score.

Equivalised household income: The OECD-modified equivalence scale will be used to adjust household income considering household size and composition [27]. Equivalised household income is calculated by dividing the after-tax household (including all the earner to the nearest £1000) by the sum of the equivalence value of all the household members (1 = first adult; 0.5 = additional adult or child >14 years old; 0.3 = child aged 0-13 years old).

Subjective SEP: The measure of the Subjective Social Status using the MacArthur Scale will be coded from 1 (lower SSS) to 10 (higher SSS).

Executive function measures

Inhibition – Stroop task: The median reaction times (RTs) will be calculated for correct responses in incongruent and congruent trials. The interference effect will be calculated as the difference between the median RTs of the incongruent trials and the congruent trials. A larger interference score is indicative of poorer inhibition. RTs data are commonly skewed, reflecting lapses of attention or eye blinks during the task [28]. To resolve this, median will be used instead of means. Median is less affected by extreme scores than the mean and provides a better estimate of central tendency for skewed distributions [29], [30]. We will also calculate the proportion of correct responses in incongruent trials because this outcome has been previously linked to the frequency of fatty food consumption [31].

Working memory – backwards digit-span task: The two-error maximum length will be calculated. It is the last digit-span a participant gets correct before making two consecutive errors and the traditional measure of a participant's backward digit span [32]. We will also calculate the maximum length i.e., the maximal backward digit span that a participant recalled correctly during all 14 trials.

Familiarity

When the answer to the question "Have you ever eaten this food?" will be 'yes', the food will be coded as familiar for a participant.

Liking

For each participant and each food a liking score from 0 to 100 will be recorded (anchors: not at all, extremely).

Health motivation in food choices

Both health and weight control motivation scores will be computed by averaging ratings for individual items in each dimension (health motivation: 6 items; weight control motivation: 4 items). They will range from 1 to 4: 1 = Not at all important; 2 = A little important; 3 = Moderately important; 4 = Very important. Cronbach's alpha will be calculated as an indicator of internal consistency in order to compare our data with the original study that developed this measure [24].

Other variables

BMI will be calculated as weight (kg) / height (m²). BMI data will be trimmed for implausible values excluding weight for less than 30 kg and more than 250 kg, height for less than 145 cm and more than 3m, BMI < 14 or BMI > 48 [33], [34].

Physical activity level will be estimated based on IPAQ-SF answers as MET-minutes per week²: self-reported physical activity in minutes*MET score [walking = 3.3, moderate intensity = 4.0, vigorous intensity = 8.0]*number of days [25].

Aim guessing: Participants who identify the aim of the study as being to examine the influence of kcal or PACE labelling on self-served food portion size will be coded as being aware of the study aims. Responses will be independently coded by two researchers, with discrepancies in coding decisions resolved by a third researcher.

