4.3. Exclusion criteria

- Having any dietary restriction:
 - Vegetarian
 - Vegan

- Gluten-free
- Sugar-free
- Diary/lactose-free
- Food allergy (e.g. milk, eggs, nut, wheat, fish, etc.)

- Taking part more than once:
Prolific is designed to avoid the same participant to take the same survey twice (i.e., one participant cannot access the study link twice). Each participant recruited on Prolific has a unique ID. If for some reasons a participant takes the survey twice, we will delete the second submission from the dataset by checking the ID duplicates. For the same reason, to avoid one participant takes the survey twice with different accounts, we will delete the second submission from the dataset by checking the IP duplicates.
- Failing an attention check (**Appendix G, item 9; Appendix H, item 10; Appendix O, item 4**).
- Completing the main task too fast, i.e., less than 2 sec per dish = less than 36 sec in total, that will be interpreted as careless or insufficient effort responding [19], [20].

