5.3. Measures of executive functions (EF)

Cognitive measures of EF

Inhibition is the ability to suppress impulsive or automatic responses (e.g., not choosing unhealthy foods). A Stroop task will be used to measure inhibition ($\approx 2\text{min.}30\text{sec.}$). In this task, participants are given colour words written in colour and are asked to indicate the colour of the word (not its meaning) by key press as fast as they can without making too many errors. The task included three types of trials:

- Congruent trials: colour word and the colour it is presented in are the same;
- Incongruent trials: colour word and the colour it is presented in are not the same;
- Control trials: coloured rectangles.

The task includes 4 colours (red, green, blue, black) \times 3 colour-stimuli congruency (congruent, incongruent, control) \times 7 repetitions = 84 trials randomly sampled.

Working memory is the ability to monitor the relevance of incoming stimuli and update information in memory as required and is implied in goal-shielding (e.g., stick to healthy eating goals). A backwards digit-span task will be used to measure working memory (≈ 7 min.). This task will require participants to repeat series of digits of increasing length in the reversed order. Depending on performance, participants move up a level or down a level. The first trial is a sequence of two visual digits. Assessment is 14 trials in total.

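### The Stroop interference score has no participant-level accuracy condition, so chance-level responding has an expected score of 0 ms and is read as good inhibition

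*Combined protocol and SAP*

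**What the plan says.** Section 5.3 describes the Stroop task: "The task includes 4 colours (red, green, blue, black"), crossed with three trial types and "7 repetitions = 84 trials randomly sampled". Participants respond "by key press as fast as they can without making too many errors". No error limit is given as a number.

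Section 7.1 defines the score. "The median reaction times (RTs) will be calculated for correct responses in incongruent and congruent trials", and then "The interference effect will be calculated as the difference between the median RTs of the incongruent trials and the congruent trials". Its direction is stated: "A larger interference score is indicative of poorer inhibition". A second measure follows: "We will also calculate the proportion of correct responses in incongruent trials". It stands beside the reaction-time score and does not qualify it. The control trials enter no planned score.

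The exclusions in 4.3 are dietary restriction, duplicate submission, "Failing an attention check", and completing the portion task too fast. Section 7.2 adds non-completion and ineligibility. It also mentions wrong answers as an example of a reason for later withdrawal, but this is not a defined Stroop rule. None of these uses Stroop performance.

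Inhibition is compared between education groups in 7.7 at the 0.01 level. That comparison also decides whether inhibition is tested as a mediator. In 7.8 inhibition is an exploratory moderator at 0.001.

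**The concern.** Restricting the medians to correct trials protects the score only if correct answers come from doing the task. With four keys, a quarter of random presses are correct, and their reaction times carry no congruency effect. The difference of medians is then centred on zero, which is the good end of the scale as the plan reads it. The accuracy measure puts the same person at the bad end, and no rule reconciles the two.

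A second kind of record also lacks a rule. Someone who answers by word meaning has no correct incongruent trial, so the interference score cannot be computed.

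Section 2 hypothesises better executive function in participants of higher SEP. Chance-level records in the interference score add noise and pull group means towards zero. If they are commoner in the lower education group, they work directly against the hypothesised difference, and inhibition may then not go forward to the mediation analysis.

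**Working it through.** **Trial counts (5.3).** 4 × 3 × 7 = 84, which reproduces the plan's total, and 4 × 7 = 28 trials per type.

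**A random presser.** With one key per colour (assumed), chance accuracy is 1/4.
- Expected correct per type: 28 × 0.25 = 7.
- Probability of no correct trial in a given type: 0.75^28 = 0.0003, so a score is almost always produced.
- Simulated score (20,000 random responders, mean RT 400 ms): mean between 0.0 and 1.3 ms. The SD is 33, 65, 119 and 158 ms for assumed RT SDs of 50, 100, 200 and 300 ms.

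**Comparison with attentive participants.** The documents give no RT distribution or Stroop effect. Assumed attentive effects of 30 to 150 ms, with between-person SD of 40 or 80 ms, were tried. A score of exactly 0 is better than 61% to 98% of attentive scores. A random presser's own noisy score beats a randomly drawn attentive score with probability 0.57 to 0.96.

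**Effect on the education comparison.** Assumptions:
- Attentive scores have mean 102 ms and SD 89 ms (simulated from a true effect of mean 100 and SD 60, trial RT SD 200, accuracy 93–97%).
- Random scores have mean 0 and SD 125 ms.
- The true education–inhibition correlation is 0.17. This is borrowed from the education–health motivation value in 7.9, because none is given for inhibition.
- The education groups are of equal size (4.1), n = 1,600.

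The true group difference is 2 × 0.17 × 60 = 20.4 ms, so the attentive group means are 102 ± 10.2, that is 112.2 (lower) and 91.8 (higher). Let eL and eH be the shares of random responders in the lower and higher groups, and e their average:
- D = (1 − eL) × 112.2 − (1 − eH) × 91.8
- V = (1 − e) × 89² + e × 125² + e(1 − e) × 102²
- r = D / (2√V)
- power = Φ(atanh(r) × √1597 − 2.576)

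Example, 8% v 2%: D = 103.22 − 89.96 = 13.26; √V = 93.8; r = 13.26/187.6 = 0.071; power = Φ(2.83 − 2.576) = 0.60.

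| Lower v higher | D (ms) | √V | r | Power at 0.01 |
|---|---|---|---|---|
| none | 20.40 | 89.0 | 0.115 | 98% |
| 1% v 1% | 20.20 | 90.0 | 0.112 | 97% |
| 1.5% v 0.5% | 19.18 | 90.0 | 0.107 | 96% |
| 5% v 5% | 19.38 | 93.8 | 0.103 | 94% |
| 10% v 10% | 18.36 | 98.1 | 0.094 | 88% |
| 7% v 3% | 15.30 | 93.8 | 0.082 | 75% |
| 8% v 2% | 13.26 | 93.8 | 0.071 | 60% |

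Full simulations under the same main assumptions agree within a few points: 73–75% at 7% v 3%, 63–65% at 8% v 2%, and 85–91% at 10% in both groups.

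**When would the sign change?** D < 0 needs (1 − eL)/(1 − eH) < 91.8/112.2 = 0.818. With eH = 2%, eL would have to exceed 19.8%.

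**What an accuracy floor does.** On the 56 congruent and control trials, a random presser reaches 50% with probability 0.00005. A participant with 80% accuracy falls below it with probability about 1 in 10 million. Someone answering by word meaning is right on all 28 congruent trials, so has at least 28/56 = 50% and always passes. A floor alone therefore misses that record.

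**The case against.** The strongest reply is that few such participants would reach the analysis. Failing an attention check removes the whole submission, and the recruitment text warns of this. Two checks are visible in the appendices: one with three options in the baseline questionnaire, and one with four in the food-motive questionnaire, which follows the executive function tasks. Someone answering at random throughout passes both with probability 1/3 × 1/4 = 1/12. If 10% of entrants did so, the residual share would be (0.10/12)/(0.90 + 0.10/12) = 0.9%, and the table shows little loss there. Section 7.9 plans for about 10% loss from dropout and failed quality controls together, so a residual 5–10% would be about as large as the whole planned loss. This stands for people careless throughout. It does not cover someone who disengages or misunderstands only on the Stroop task, and the documents give no rate for that.

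The second inhibition measure would also make chance-level performers visible. That is true, but it does not repair the reaction-time score.

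The 0.17 is borrowed from another construct, and trial noise alone lowers it to 0.115, a larger loss than any scenario in the table adds. Both points stand and limit what can be said about size.

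A reader might infer that the score could reverse the education difference. The documents do not support this: r stays positive in every scenario examined, and under these assumptions a reversal needs about 20% v 2%. A reader might also infer that each random presser scores close to 0 ms. That is only the expected value, since a single score rests on about 7 correct trials per type.

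**Conclusion.** The point holds as a cheap improvement to a stated scoring rule. Applied as written, 7.1 gives chance-level responders an expected score at the favourable end of the scale, contradicts its own accuracy measure for the same people, and yields no score for those who answer by word meaning. That random pressers tend to look better than attentive participants needs only a positive typical interference effect, which the scoring already presupposes.

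The consequence is dilution of the education difference in inhibition, and more of it if chance-level responding is commoner in the lower education group. The loss is negligible at around 1%. It is material (power roughly 55–75%) only at shares such as 7% v 3% or 8% v 2%, for which the documents give no basis. The primary analysis of self-served energy is untouched. The mediation step runs only if the labelling-by-education interaction is significant, and the moderator use is exploratory.

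**What to change.** Add to the Stroop paragraph in 7.1, before data are seen:

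- (a) Both inhibition measures are set to missing for participants whose accuracy on the 56 congruent and control trials is not clearly above the 25% chance level, for example below 50%.
- (b) The interference score alone is also set to missing when a participant has fewer than a stated minimum number of correct trials in either the congruent or the incongruent type. This covers those who answer by word meaning; their incongruent accuracy is kept.

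Apply both rules only to the inhibition analyses in 7.7 and 7.8, keep these participants in the main analysis, and report the numbers affected by education group.

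The cost is a sentence or two, using responses that the task already produces. A few participants are lost from secondary and exploratory analyses. The exact cut-offs are a choice, so they should be fixed in advance.

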7.2. Missing data

We do not anticipate missing data on the primary outcome and dependant variables because the online study will not allow missing answers. Data from participants who start but not finish the study will not be analysed. Submissions of participants who fail the attention checks or do not pass eligibility criteria will not be analysed. Any *a posteriori* withdrawal will be reported and reasons for withdrawal will be documented (e.g. incorrect answers, technical problems).

7.3. Participant's characteristics

We will report the baseline characteristics overall and for participants of lower and higher education including gender, age, ethnic group, employment status, highest educational qualification, years in higher education, equivalised household income, subjective socioeconomic status, BMI, dieting status and physical activity in MET-minutes for vigorous-intensity activity, moderate-intensity activity, walking and in total. Continuous variables will be summarised using means and standard deviations and differences between the two groups will be tested using t-tests. Categorical variables will be summarised using counts and percentages and differences between the two groups will be tested using Chi-square tests.

7.4. Familiarity and liking

We will report the percentage of dishes that participants are familiar with and the average liking score across foods overall and for participants of lower and higher education. Differences in familiarity between the two groups will be tested using Chi-square tests and differences in liking using t-tests.

7.5. Main analyses

The primary aim of the statistical analyses will be to test the effect the labelling intervention and SEP on self-served energy. Secondary analyses will be run in order to investigate the role of potential mediators to explain the relationship SEP-self-served energy. The measure of SEP used in our main analyses will be the *highest educational qualification* (binary variable: *lower vs. higher*) because previous research showed that people of higher education were more likely to use nutrition labels [35], [36].

² MET-minutes: Metabolic Equivalent of Task of an activity × minutes performed.

Linear mixed effect models will be run in order to test the effect of the labels and of highest educational qualification on the self-served energy, with participants and dishes set as random effects to account for correlation between repeated measures by the same participant and across the different food items. The main model will test the effect of the labelling intervention (four levels: kcal labelling, PACE labelling, kcal and PACE labelling, no labelling), highest educational qualification (two levels: lower, higher) and the interaction between labelling intervention and highest educational qualification. If the interaction is significant, analyses will be stratified by *highest educational qualification (lower and higher)* and two linear mixed models will be fitted to examine the effect of the labelling intervention on self-served energy.

If there is a main effect of the labelling intervention in one of the above linear mixed models we will follow up this main effect by conducting the following pairwise comparisons:

- Self-served energy in each of the three labelling conditions compared to no labelling condition:
 - o No labelling vs. kcal labelling
 - o No labelling vs. PACE labelling
 - o No labelling vs. kcal and PACE labelling combined
- Self-served energy in the combined labelling condition compared to single labelling conditions
 - o Kcal and PACE labelling combined vs. kcal labelling
 - o Kcal and PACE labelling combined vs. PACE labelling
- Self-served energy in one single labelling condition compared to the other single labelling condition:
 - o Kcal labelling vs. PACE labelling

We will apply a Bonferroni correction to the level of significance based on the number of pairwise comparisons made (e.g., 12 comparisons: $0.05/12=0.004$).

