4. PARTICIPANTS AND RECRUITMENT

4.1. Recruitment

Participants will be recruited through Prolific, an online recruitment platform in which participants are compensated proportionate to the time it takes to complete the online study ($\approx 5\text{£}/\text{hour}$ reward participants). Participants' recruitment will be stratified by gender (50% male, 50% female), student status (3.5% yes and 96.5% no) [18] and qualification levels (50% A level or below, 50% above A level) in order to recruit participants of lower and higher SEP.

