7.6. Sensitivity analyses

We will conduct sensitivity analyses to examine whether the pattern of results from the main analyses differ when:

- excluding the aim guessers from the main analyses, or if more than 20% of participants guess the aim of the study, including an 'aim guessing' variable (two levels: yes, no) as a covariate in the main model;
- substituting highest educational qualification by level of education (composite score) in the main model;
- including hunger and liking as covariates in the main model as these two variables are likely to influence how much one serves oneself of a dish;
- excluding any dish that is familiar to less than 50% of participants or that is scored < 50 in liking on average (mid-way of the scale) to examine whether results are consistent when only well liked and familiar foods are used.

We will report whether sensitivity analyses result in deviations from the pattern of significance to the main analyses (i.e., any significant differences between conditions becoming not significant, and vice versa).

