16. APPENDIX G: BASELINE QUESTIONNAIRE

1. *Gender*

- Male
- Female
- Other

2. *Age*

- __ (free text; range of 18-99)

3. *Ethnicity*

- White
- Black
- Asian
- Mixed
- Other

4. *What is your current employment status?*

- Full or part-time
- Student
- Retired
- Temporary or permanently sick or disabled
- Looking after home/family
- Other unemployed

5. *What is your highest educational qualification? If you are a student please select the diploma being studied for.*

- No qualification
- 1-3 GCSEs
- 4+ GCSEs
- A level
- CertHE
- DipHE
- Higher education or Bachelor's degree
- Post-Graduate degree
- Doctoral or professional degree

6. *After leaving school (i.e. at 16 years old), how many further years of higher education (i.e. a formal course) did you study for?*

Examples:

If you left school and did not go on to study further in higher education, your answer would be 0.

If you left school and then studied for two years for A levels, your answer would be 2.

If you completed A levels over two years and then also studied for a three-year undergraduate degree, your answer would be 5.

- __ (free text)

7. *What is your annual household income (after tax), including all earners in your household, in GBP (to the nearest £1000)?*

[figure not shown]
£_____ (free text; range 0-999,999)

8. How many adult(s) or child(ren) aged 14 and over live at your house, including you?
__ (free text; range of 1-20)

9. How many child(ren) aged under 14 live at your house, including you?
__ (free text; range of 1-20)

10. This is an attention check. How many times have you visited the planet Mars?
 Several times
 Just once
 Never

11. Think of a ladder (see the image below) as representing where people stand in society. At the top of the ladder are the people who are best off—those who have the most money, most education and the best jobs. At the bottom are the people who are worst off—who have the least money, least education and the worst jobs or no job. The higher up you are on this ladder, the closer you are to people at the very top and the lower you are, the closer you are to the bottom. Where would you place yourself on the ladder?

Choose the number whose position best represents where you would be on this ladder:

1 2 3 4 5 6 7 8 9 10

12. Are you currently dieting?
 Yes
 No

13. Weight

Select the unit:

- kg
- st and lb

— — —

14. Height

Select the unit:

- cm
- ft and in

— — —

15. *How hungry do you feel?*

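### The main model omits gender and baseline hunger, and the only hunger-adjusted model also conditions on a liking rating taken after the labels

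*Combined protocol and SAP*

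**What the plan says.** Section 7.5 describes a linear mixed model with participants and dishes as random effects. On the fixed part it says: "The main model will test the effect of the labelling intervention" (four levels), binary education and the label-by-education interaction. If the interaction is significant, "two linear mixed models will be fitted to examine the effect of the labelling intervention on self-served energy", one in each education group. On the follow-up contrasts: "We will apply a Bonferroni correction to the level of significance based on the number of pairwise comparisons made", with 0.05/12 as the example.

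Section 7.6 lists a sensitivity analysis "including hunger and liking as covariates in the main model as these two variables are likely to influence how much one serves oneself". This is the only planned use of hunger in a model.

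On timing, the study flow in section 6 says: "Participants will complete a baseline questionnaire on demographics", and places this before the meal task. Appendix G shows that the questionnaire holds gender (item 1) and "How hungry do you feel" (item 15). The flow places the familiarity and liking ratings after the meal task, the executive function tasks and the motivation and activity questionnaires.

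Gender is a 50/50 recruitment quota in 4.1 and a descriptive characteristic in 7.3. Sections 7.6 and 7.7 replace education by other measures of socio-economic position (SEP: the composite score, income, subjective status), and 7.8 replaces it by cognitive, motivation and activity measures. None of these models names gender.

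**The concern.** Two things are at stake.

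**Precision.** The plan expects hunger to affect serving, and it balances recruitment on gender. Both are known before exposure. Leaving them out of the main model puts whatever variance they explain into the error of every label contrast. The sample size in 7.9 is set at 0.05, whereas the pairwise tests in 7.5 use a Bonferroni-corrected level, so there is little precision to spare.

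**Interpretation of the hunger adjustment.** Liking is rated after participants have worked through 18 dishes with or without labels, so the labels could affect it. The documents give no evidence that they do. If significance changes in the joint model, which 7.6 undertakes to report, the reader cannot tell whether hunger or conditioning on a post-exposure rating caused the change.

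Bias in the randomised label contrasts is not at stake. Education is not randomised, and the gender and education quotas are listed separately without saying that they are crossed. Gender could therefore be unevenly spread over the education groups, and no planned model would show whether the education terms are sensitive to that.

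**Working it through.** **Inputs.** From 7.9: SD 300 kcal at trial level and at participant level, 18 trials per participant, 1,600 participants (400 per arm), alpha 0.05, power 0.80. Two-sided testing is assumed. From 4.1: half the sample in each education group, so about 200 per label-by-education cell. From 7.5: six pairwise contrasts, or twelve over two strata.

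**The plan's own figure.** The variance of a participant's 18-dish mean is 300² + 300²/18 = 90,000 + 5,000 = 95,000. The SE of a label contrast at 400 per arm is √(2 × 95,000/400) = 21.79 kcal. The difference detectable with 80% power at 0.05 is (1.960 + 0.842) × 21.79 = 61.1 kcal. The stated 8% cannot be reproduced directly because no control mean is given; 61.1 kcal is 8% of about 763 kcal. I therefore use 61.1 kcal as the reference difference, defined by its 80% power under the plan's SDs.

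**Effect of adjustment.** Participant-level covariates can reduce only the 90,000. With R² the share of it explained, V = 90,000 × (1 − R²) + 5,000. R² is not in the documents. I assume 5–20% for gender and hunger together (multiple correlation 0.22–0.45).

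Power = Φ(61.1/SE − z), with z = 1.960 at 0.05, 2.638 at 0.05/6 and 2.865 at 0.05/12.

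| | Unadjusted | R² 5% | R² 10% | R² 20% |
|---|---|---|---|---|
| V | 95,000 | 90,500 | 86,000 | 77,000 |
| SE ratio √(V/95,000) | 1 | 0.976 | 0.951 | 0.900 |
| SE, 400 per arm = √(2V/400) | 21.8 | 21.3 | 20.7 | 19.6 |
| Power at 0.05 | 0.800 | 0.819 | 0.838 | 0.875 |
| Power at 0.05/6 | 0.565 | 0.592 | 0.620 | 0.682 |
| SE, stratified, 200 per arm = √(2V/200) | 30.8 | 30.1 | 29.3 | 27.7 |
| Stratified power at 0.05/12 | 0.188 | 0.202 | 0.217 | 0.253 |
| Stratified detectable difference = (2.865 + 0.842) × SE | 114.3 | 111.5 | 108.7 | 102.9 |
| SE of a difference in label effect between education groups = √(4V/200) | 43.6 | 42.5 | 41.5 | 39.2 |

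SEs and differences are in kcal.

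**Gender alone.** Assume that men serve 10–25% more than women around an overall mean of 600 kcal, a gap of 57–133 kcal. With equal numbers, R² = (gap/2)²/300² = 0.009–0.049. The SE falls by 0.4–2.4%, and power moves from 0.800 to 0.803–0.819 at 0.05 and from 0.565 to 0.570–0.591 at 0.05/6. Any larger gain would have to come from hunger.

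**The case against.** The strongest reply is that nothing is broken. An unadjusted main model in a randomised comparison of 400 per arm is a legitimate choice, and the plan nowhere promises adjustment. The gain rests on an R² that the documents do not supply, and at the low end it is two power points. All of this stands, and it limits the point to an efficiency recommendation.

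A second reply is that hunger is already covered in 7.6, whose purpose is to see whether the pattern of results changes and not to attribute a change to one covariate. The purpose is fairly stated. But a model that mixes a pre-exposure and a post-exposure variable cannot say why a pattern changed, and separating them costs one extra model.

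A third reply is that hunger may lie partly downstream of SEP, so adjusting could remove part of the education main effect. This stands. The hypotheses in section 2 about self-served energy, however, concern label effects and their difference by SEP, and the unadjusted estimate would still be reported.

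It can also be said that the gender-only gap is set around 600 kcal while the 8% target implies about 763 kcal. The reference difference is not 8% of any mean, so the two do not conflict. If 8% of 600 = 48 kcal is used throughout, unadjusted power is about 60% and rises to 62–69% for R² of 5–20%, which is a gain of similar order.

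Two further limits apply. Gender is a sampling quota and not a randomisation stratum, so the usual argument for adjusting for allocation factors does not apply. The moderated-mediation diagrams are not visible, so the absence of gender there rests on the text.

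**Conclusion.** The concern holds. Gender is in no model described in 7.5 to 7.8, and hunger appears only jointly with a post-task rating. Hunger is recorded after allocation, because the flow lists randomisation first, but before any label or task instruction, so it is a sound covariate for the label contrasts.

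The cost is lost precision of unknown size: a 2.4–10.0% smaller SE if the two variables explain 5–20% of between-participant variance, and almost nothing if only gender matters and its effect is small. Adjustment does not rescue the education-stratified pairwise step, which is underpowered for a 61 kcal difference either way. Confidence is medium, because the facts are clear but the gain depends on an assumed R². The change is worth making because it must be fixed before data are seen and uses variables already collected.

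**What to change.** - **Section 7.5:** prespecify gender and baseline hunger as fixed effects in the main model and in the education-stratified models. State how the Other response to gender is coded, for example as a third level.
- **Unadjusted model:** report it as a sensitivity analysis, and read the education main effect alongside it.
- **Section 7.6:** run the liking-adjusted model separately and label it as adjusting for a post-exposure rating.
- **Optional:** add a sensitivity model with a gender-by-label term, to see whether the label-by-education interaction is sensitive to gender.

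The cost is SAP wording and one or two more models to report; no data collection changes.
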